The protocol, informed consent form(s), recruitment materials, and all participant materials will be submitted to the IRB for review and approval. Approval of both the protocol and the consent form must be obtained before any participant is enrolled. Any amendment to the protocol will require review and approval by the IRB before the changes are implemented to the study. All changes to the consent form will be IRB approved; a determination will be made regarding whether a new consent needs to be obtained from participants who provided consent, using a previously approved consent form.]

1 PROTOCOL SUMMARY

1.1 SYNOPSIS

Title:	A Phase 4 Study to Assess the Clinical Efficacy of H.P. Acthar Gel 80 U/ml to Improve the Signs and Symptoms in Subjects with Dry Eye Disease
Study Description:	This study will test the efficacy of a systemic intervention and adrenocorticotropin injection for severe dry eye unrelieved by traditional dry eye treatments.
Objectives:	The primary objective of the study is to investigate the safety and efficacy of H.P. Acthar gel injections in subjects who have a documental clinical diagnosis of dry eye disease. Secondary objective is to demonstrate safety for use of Acthar H.P. Gel in dry eye subjects.
Endpoints:	Primary Endpoint: Improvement of patient comfort over the length of the study using a validated dry eye comfort questionnaire, OSDI and improvement of spk in cornea over study treatment period Secondary Endpoints: conjunctival staining with lissamine green
Study Population:	12 study subjects 18-85 will be enrolled with male or female in the Nashville, TN area who are generally healthy but have persistent signs and symptoms of dry eye diseases after treatment with traditional dry eye treatments including but not limited to: IPL, cyclosporing, lifitegrast, loteprednol, artificial tears and warm compresses
Phase:	4

Description of *Single site study in Nashville, TN and surrounding areas.*

Sites/Facilities Enrolling

Participants:

Description of Study *Acthar is an adrenocorticotropic hormone given subcutaneously twice*

Intervention: *weekly.*

[figure not shown]
Study Duration: *6 months*

Participant Duration: *12 weeks*

1.2 SCHEMA

Example #1 Flow diagram (e.g., randomized controlled trial)

Prior to
Enrollment

Example #3 provided as a guide, customize as needed: Timeline diagram (e.g., randomized controlled trial)

1.3 SCHEDULE OF ACTIVITIES (SOA)

u

Procedures	Screening Day -7 to -1	Enrollment/Baseline Visit 1, Day 1	Study Visit 2 Day 7 +/-1 day	Study Visit 3 Day 14 +/-1 day	Final Study Visit 13 Day 84 +/-1 day
Informed consent	X				
Demographics	X				
Medical history	X				
Randomization	X				
Administer study intervention		X			
Concomitant medication review	X	X----- -----X			
Bcva	X	X	x	x	X
Slit lamp biomicroscopy	X	x	x	x	x
IOP	X	X	x	X	X
Corneal fluorescein stain	X	X		X	X
Conjunctival liissamine stain	X	X		X	X
	X	X		X	X
anesthetized schirmer	X	X		x	x
Dilated ophthalmoscopy	X				x
Training on study medications	X				
Dispense study meds					
\	X				

2 INTRODUCTION

2.1 STUDY RATIONALE

Many people suffer from dry eye disease and are incompletely relieved of signs and symptoms with traditional treatments like artificial tears, warm compresses, prescription eye drops, and IPL. Those most severely affected may find relief using a systemic medication that increases the body's endogenous production of corticosteroid to reduce surface inflammation. This study will attempt to demonstrate improvement in both signs and symptoms of dry eye and the safety of use of this medicine in patients suffering with moderate to severe dry eye.

2.2 BACKGROUND

Acthar is approved by the FDA for the treatment of severe allergic and inflammatory eye conditions. Dry eye disease is a disease that affects millions of Americans and may be underdiagnosed. Dry eye disease is diagnosed by evaluating the signs and symptoms of dry eye including self-reported ocular comfort and staining of both the cornea and the conjunctiva by special stains. Moderate to severe dry eye disease is characterized by a self-perpetuating and progressive increase in inflammation of the ocular surface. For patients that continue to experience bothersome symptoms and/or loss of function due to dry eye despite compliance with current and traditional therapies, the use of corticotropin hormone may offer some relief.

2.3 RISK/BENEFIT ASSESSMENT

2.3.1 KNOWN POTENTIAL RISKS

Known risks of Acthar use include
Infections
Cushing's syndrome
High blood pressure
Bleeding stomach ulcers
Irritability
Depression
Insomnia
Mood swings
Loss of diabetic control
Cataracts
Glaucoma
Allergy to acthar
Long term use can affect children's growth and development
Osteoporosis
Birth defects

The most common side effects are

Increased blood sugar

Increased blood pressure

Fluid retention

Changes in appetite

Weight gain

Cardiac hypertrophy

2.3.2 KNOWN POTENTIAL BENEFITS

By activating the release of endogenous cortisol and impacting steroid independent immunomodulatory and anti-inflammatory pathways, Acthar reduces inflammation in the body without synthetic steroids. Immediate benefits in dry eye disease would be reduced symptomatology and improvement of function which would be expected to extend long term and help to prevent and reduce future damage from chronic inflammation.

2.3.3 ASSESSMENT OF POTENTIAL RISKS AND BENEFITS

Moderate to severe dry eye can cause significant discomfort and interfere with even daily normal function. Patients can experience depression, reduced function at work, social anxiety if others incorrectly interpret red eyes as staying out too late, use of illegal drugs or episodes of crying. Patients who have exhausted all currently available therapies and still experience bothersome signs and symptoms especially if symptoms interfere with jobs and normal daily function may feel that the increased risk of systemic anti-inflammatory may be worth the benefits of reduced ocular surface inflammation.

3 OBJECTIVES AND ENDPOINTS

OBJECTIVES	ENDPOINTS	JUSTIFICATION FOR ENDPOINTS
Primary		
The primary objective is the efficacy of H.P. Acthar gel injections in subjects with documented moderate to severe dry eye disease who have failed traditional therapies.	The primary endpoint(s) are improvement in comfort over the course of the trial with a validated dry eye comfort questionnaire, OSDI and improvement in the number of corneal spk using fluorescein stain over the course of the trial.	Both endpoints have been validated in recent dry eye approvals (lifitegrast).
Secondary		
The secondary objective is improvement in conjunctival staining with lissamine green and demonstration of safety of use of in dry eye subjects.	Conjunctival staining with lissamine green is another method of measuring ocular surface inflammation and safety will be measured by collecting intraocular pressure, assessing AEs, slit lamp biomicroscopy, BCVA and dilated ophthalmoscopy	Lissamine green staining has also been used in recent approvals (lifitegrast) and safety of adrenocorticotrophic stimulators must measure common side effects of steroid like glaucoma, cataract and potential change in vision.
.	.	

4 STUDY DESIGN

4.1 OVERALL DESIGN

- The hypothesis is that use of H.P. Acthar gel subcutaneously has the ability to reduce ocular surface inflammation in moderate to severe dry eye and improve the signs and symptoms over the course of the trial.*
- Single site pilot study Pilot study*

- *H.P. Acthar gel will be dosed two or three times weekly to control signs and symptoms at the discretion of the primary investigator.*
- *One study arm of active intervention for up to 89 days*
- *Single site*
- *Study intervention is use of H.P. Acthar Gel)*
- *No interim analysis is planned*

There are no planned stratifications.

4.2 SCIENTIFIC RATIONALE FOR STUDY DESIGN

This is a small single site study with no control designed to show efficacy in moderate to severe dry eye disease which may be used in the future as a basis for a larger, multi-site, randomized placebo controlled study. Potential pitfalls include the small number of participants, the variable nature of the disease and the often inverse relationship of signs to symptoms in dry eye disease.

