6.3 MEASURES TO MINIMIZE BIAS: RANDOMIZATION AND BLINDING

All subjects will receive active drug with no control.

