9.2 SAMPLE SIZE DETERMINATION

This is a small pilot study of 12 participants completing the study assessments. There is no placebo and it is not powered to show statistical significance.

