## Statistical Analysis Plan Acthar Pilot Study

The statistical analysis plan for this study includes analysis of patients completing the trial and measuring the change from baseline to final visit including intervisit changes. For each of these time points, P-values will be collected, standard deviations, standard error means, 95% confidence intervals of the difference and 2-tailed t test applied. There is no placebo or control in this study and the number of participants was not powered to show statistical differences.

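### Efficacy is the stated aim, but change from baseline in a single arm without a comparator cannot separate drug effect from non-drug change

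*Protocol*

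**What the plan says.** Efficacy is the declared aim in several places. Protocol 4.2 states: "This is a small single site study with no control designed to show efficacy in moderate to severe dry eye disease". Protocol 3 states: "The primary objective is the efficacy of H.P. Acthar gel injections in subjects with documented moderate to severe dry eye disease". The study title and the objectives in 1.1 are also about efficacy, and the hypothesis in 4.1 credits the drug with reducing inflammation and improving signs and symptoms.

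The design has one arm. Protocol 6.3 says: "All subjects will receive active drug with no control". Protocol 9.1 defines the primary result as mean improvement from baseline to the final visit in corneal staining and the symptom score. No target value, historical reference or external control is given.

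The limits are partly disclosed. Protocol 9.2 says "There is no placebo and it is not powered to show statistical significance", and the SAP says "There is no placebo or control in this study and the number of participants was not powered to show statistical differences". Section 4.1 calls the trial a pilot. Section 4.2 foresees a later randomised placebo-controlled study and lists three pitfalls: few participants, variable disease, and signs that often run opposite to symptoms. Placebo response and regression to the mean are not listed.

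The two documents differ on the analysis. Protocol 9.4.2 plans descriptive statistics. The SAP plans P-values, 95% confidence intervals and two-tailed t tests on change from baseline and between visits.

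**The concern.** An efficacy objective asks what the drug did compared with what would have happened without it. This design observes only what happened. A t test of change from baseline tests whether the mean change is zero, which is a different question.

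Several features of this protocol make non-drug improvement plausible. Entry requires at least 40 mm on the discomfort scale and at least 5 spk (5.1), so participants are selected on high values. Rescue medication may be used at any time (6.5.1), and the analysis sections give no rule for it. Participants know that they receive active drug, and the primary symptom measure is self-reported.

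At stake is the reading of the primary result. A significant fall could be taken as meeting the stated objective although the drug did nothing. What the trial can properly deliver, the size and spread of change for planning the controlled study, is not among its objectives.

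**Working it through.** **The plan's own figure.** Protocol 9.2 gives 12 completers: "This is a small pilot study of 12 participants completing the study assessments". This number cannot be re-derived, because no effect size, SD, power or alpha is stated. The protocol says the trial is not powered, so this is not a calculation error.

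**What the primary result estimates.** Expected change = drug effect + placebo response + natural course + regression to the mean + effect of rescue medication. One arm gives one mean, and only the sum can be estimated. A larger n would shrink the standard error of the sum but would not split it into its parts.

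**How often the SAP's test would be significant with zero drug effect.**
- n = 12 (Protocol 9.2), so df = 11.
- Alpha is not stated. Two-sided 0.05 is inferred from the SAP's 95% intervals and two-tailed test. Critical value 2.201.
- d = mean non-drug improvement divided by the SD of the change score. The values are assumed, because the documents give none.
- Under these inputs the statistic follows a noncentral t with noncentrality d × √12, and P(significant improvement) = P(T > 2.201).

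| Assumed d | d × √12 | P(significant improvement) |
|---|---|---|
| 0 | 0 | 2.5% |
| 0.25 | 0.866 | 12.2% |
| 0.5 | 1.732 | 35.3% |
| 0.8 | 2.771 | 71.4% |
| 1.0 | 3.464 | 88.3% |

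**Precision.** 95% CI half-width = 2.201 / √12 = 0.635 SD of the change score.

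**One component alone: regression to the mean from the 40 mm threshold.** Assume a bivariate normal score with population mean μ, SD σ and test-retest correlation ρ, no drug effect, and the qualifying value used as baseline. With z = (40 − μ)/σ and λ = φ(z)/[1 − Φ(z)], expected spurious improvement = (1 − ρ) × σ × λ.
- μ = 40, σ = 25, ρ = 0.5: z = 0, λ = 0.798, improvement = 0.5 × 25 × 0.798 = 10.0 mm.
- μ = 60, σ = 20, ρ = 0.9: z = −1, λ = 0.288, improvement = 0.1 × 20 × 0.288 = 0.6 mm.

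These are the extremes over μ 40 to 60, σ 20 to 25 and ρ 0.5 to 0.9. Simulated trials of 12 over the same range gave a significant improvement in 4% to 28% of cases, against 2.5%. If baseline is measured separately after screening, part of the regression occurs before baseline and these figures fall.

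**The case against.** The strongest reply is that this is an openly uncontrolled pilot, which is a legitimate design. The sentence in 4.2 goes on to present the study as a possible basis for a controlled one. Section 9.1 already frames the primary result as a change from baseline, Section 9.4.2 is descriptive, and the SAP already plans the standard deviations and confidence intervals that a planning study needs. The probabilities above are generic properties of a one-sample t test at assumed effect sizes, not estimates for this trial.

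Much of this stands. A reader might infer that non-drug change would be reported as drug efficacy. The documents do not support that: they plan no such report and define no target value or rule for declaring efficacy. Section 10.1.2 lists demonstrated efficacy as a possible ground for ending the study, but gives no criterion. A reader might also infer that nothing in the documents tempers the conclusion. That is too absolute, given the disclosures in 4.1, 4.2, 9.2 and the SAP. Nor does the lack of power cause the problem, since a large single-arm trial would have it too.

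What does not stand is the idea that disclosure settles the matter. Saying that a trial is not powered warns that a real effect may be missed. It does not warn that a change may be credited to the drug without grounds. The SAP's P-values make that misreading easier.

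**Conclusion.** The point holds as a mismatch between the stated aim and what the design can show. The aim is wrong as written; the choice of an uncontrolled pilot is not. The exact statement is that drug effect could not be separated from non-drug change.

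The size depends on assumptions. If non-drug improvement lies between 0.25 and 1.0 SD of the change score, the SAP's test would be significant in 12% to 88% of trials of an inert drug. These sizes, and the inputs to the regression-to-the-mean figures, are illustrative. The conclusion does not rest on them, because it follows from having no comparator.

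Severity is moderate. No data, visit or calculation is invalid, and the estimates remain usable for planning. The wording of the objective and the status of the tests should still be corrected before results are interpreted.

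**What to change.** 1. In Protocol 1.1 (title and objectives), 3, 4.1, 4.2 and 9.1, restate the aim, for example: *to estimate the mean within-participant change from baseline to the final visit in the symptom measure and corneal spk, and the SD of that change, with 95% confidence intervals, in order to plan a randomised placebo-controlled study.*
2. In Protocol 9.4.2 and the SAP, add: *change from baseline will not be attributed to Acthar, because this design cannot separate drug effect from placebo response, natural course, regression to the mean or rescue medication; any P-values are descriptive and are not evidence of efficacy.* This also reconciles the SAP's tests with the descriptive analysis in 9.4.2.
3. Add placebo response and regression to the mean to the pitfalls in 4.2.

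A control arm within the same 12 participants would not rescue the efficacy aim. By the normal approximation at two-sided 0.05, six per arm gives power Φ(d√3 − 1.96): about 14% for an assumed drug-versus-control difference of 0.5 SD and 41% for 1.0 SD. For 80% power, n per arm = 2 × (1.96 + 0.84)² / d², or 63 and 16 at those differences.

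The cost is protocol and SAP wording only, with no added participants, visits or data. The stated claim becomes less favourable.

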4.3 JUSTIFICATION FOR DOSE

H.P. Acthar gel will be injected subcutaneously two or three times weekly. Subjects will self-administer the dose recommended by the treating physician which may range from 80 international units two to three times per week. Nursing support from Mallinkrodt to train study coordinator and study personnel who will train subjects on proper administration techniques will be available at all times points in the study. Patients will self-inject the study medicine for the length of the study, 12 weeks.

4.4 END OF STUDY DEFINITION

A participant is considered to have completed the study if he or she has completed all phases of the study including the last visit or the last scheduled procedure shown in the Schedule of Activities (SoA), Section 1.3.

5 STUDY POPULATION

5.1 INCLUSION CRITERIA

In order to be eligible to participate in this study, an individual must meet all of the following criteria:

1. Provision of signed and dated informed consent form and HIPPA authorization.
2. Stated willingness to comply with all study procedures and availability for the duration of the study
3. Male or female, aged 18 and older.
4. Diagnosed with moderate to severe dry eye in one or both eyes.
5. History of persistent symptoms despite use of artificial tears and one or more of the following ophthalmic drops: loteprednol, cyclosporine or lifitegrast.
6. At least 40 mm on the ocular discomfort scale.
7. At least 5 spk on one or both corneas.

8. A grade of 1 or greater in the nasal or temporal areas of one or both eyes.
9. Have normal lid anatomy.
10. Ability to take subcutaneous injected medication and be willing to adhere to the study regimen
11. For females of reproductive potential: use of highly effective contraception for at least 1 month prior to screening and agreement to use such a method during study participation and for an additional 4 weeks after the end of Acthar administration
12. For males of reproductive potential: use of condoms or other methods to ensure effective contraception with partner
13. Are postmenopausal (no menstrual cycle for at least one year prior to Visit 1) or have undergone bilateral tubal ligation, hysterectomy, hysterectomy with uni or bilateral oophorectomy, or bilateral oophorectomy.

5.2 EXCLUSION CRITERIA

An individual who meets any of the following criteria will be excluded from participation in this study:

1. Have a known hypersensitivity or contraindication to the investigational product or their components.
2. Have used topical or nasal vasoconstrictors within 14 days prior to screening.
3. Pregnancy or lactation
4. Subjects can be on the following medications if they have been on a stable dose for 12 weeks: topical cyclosporing, topical lifitgrast and/or topical loteprednol etabonate. Tetracycline compounds, omega 3s, anticholinergics, anticonvulsants, antidepressants, retinoids, systemic immunosuppressive agents including oral corticosteroids, non-steroidals, antihistamines, or mast cell stabilizers, punctal plugs, contact lens wear and glaucoma medications.
5. Subjects must be unwilling to abstain from eyelash growth medications for the duration of the trial.
6. Subjects must not have had penetrating intraocular surgery, refractive surgery or corneal transplantation, eyelid surgery within 12 weeks prior to Visit 1.
7. Febrile illness within one week.
8. Treatment with another investigational drug or other intervention within *one month*.
9. *Subjects with a history of herpetic keratitis.*
10. Have serious or severe disease or uncontrolled medical condition that in the judgement of the investigator could confound study assessments or limit compliance.

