6.5 CONCOMITANT THERAPY

For this protocol, a prescription medication is defined as a medication that can be prescribed only by a properly authorized/licensed clinician. Medications to be reported in the Case Report Form (CRF) are concomitant prescription medications, over-the-counter medications and supplements.

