6.5.1 RESCUE MEDICINE

The study site will not supply rescue medication.

The use of rescue medications is allowable at any time during the study and the date and time of rescue medication administration as well as the name and dosage regimen of the rescue medication must be recorded.

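### Background eye treatments must be stable only before entry and rescue is unrestricted, with no rule for values recorded after such a change

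*Protocol*

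**What the plan says.** **Entry.** Protocol section 5.2, criterion 4, reads "Subjects can be on the following medications if they have been on a stable dose for 12 weeks" and names topical cyclosporine, lifitegrast and loteprednol, the last a corticosteroid. A second sentence without a verb follows. It lists further treatments, among them "systemic immunosuppressive agents including oral corticosteroids" and "punctal plugs, contact lens wear and glaucoma medications", and does not say whether they are allowed or excluded. Inclusion criterion 5 in section 5.1 asks for "History of persistent symptoms despite use of artificial tears and one or more of the following ophthalmic drops: loteprednol, cyclosporine or lifitegrast".

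**During treatment.** Section 6.5 says "Medications to be reported in the Case Report Form (CRF) are concomitant prescription medications, over-the-counter medications and supplements"; it records and restricts nothing. Section 6.5.1 says "The use of rescue medications is allowable at any time during the study". It requires the rescue drug, its regimen, and the date and time to be recorded, but gives no permitted list, prohibited list or trigger.

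**Analysis.** Section 9.1 aims at mean improvement from baseline to final visit in symptoms and corneal staining (primary) and conjunctival staining (secondary), and at unchanged intraocular pressure (IOP). Sections 9.4.2 and 9.4.3 plan descriptive statistics. The SAP plans two-tailed t tests and 95% confidence intervals on change in participants who complete. Section 6.3 confirms that there is no control.

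**The concern.** Participants are selected because symptoms persist on at least one of the listed drops, so all 12 could be using one at entry. Over 12 weeks some may have a drop raised, another added, or a rescue drug started. If that drug is anti-inflammatory, it acts on the same symptoms and staining that serve as endpoints. Without a control arm and without an analysis rule, the resulting improvement goes into the baseline-to-final change attributed to Acthar.

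A smaller version applies to IOP. Section 3 says that "safety of adrenocorticotrophic stimulators must measure common side effects of steroid like glaucoma". A pressure-lowering drug added during the study helps produce the unchanged final IOP that section 9.1 hopes to show.

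Section 4.2 says the results may support a larger randomised trial, so a mean change partly due to other treatment could mislead that decision.

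**Working it through.** The plan gives no figure to reproduce here: no SD, effect size or rescue rate stands behind the 12 participants. The check is a reading of the text, followed by an illustration of scale.

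**1. Does any text hold background treatment fixed on study?**
- Criterion 4 looks back from entry. Criterion 5 beside it, on eyelash growth products, is worded to cover the whole trial, so on-study wording was used elsewhere but not here.
- The statement in section 6.1.2 that dosing stays consistent concerns Acthar.
- Sections 6.5 and 6.5.1 record use and set no limit.
- Section 7.2 lets the investigator withdraw someone who newly meets an exclusion criterion. This is optional and is not an analysis rule.

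**2. Does any text handle the later values?** Section 9.4.2 provides imputation for missing data, but values after rescue are observed, not missing. Section 9.4.3 and the SAP are silent.

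**3. Scale, for illustration.** From the documents: n = 12 (section 9.2), a two-tailed t test (SAP; the 5% level is implied by the 95% interval), and a 100 mm dryness line (section 8.1). Section 8.1 asks for the line at Visits 1 to 3 only, while section 9.4.2 says every visit; a Day 84 value is assumed. Assumed, because the documents give none: k participants starting or raising an anti-inflammatory, a gain of d mm each, and the SD of change.

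- Mean shift = k × d / 12. For k = 3 and d = 10, 20, 30: 2.5, 5.0, 7.5 mm.
- Mean change needed for significance = 2.201 × SD / √12 = 0.635 × SD. For SD 20, 25, 30 mm: 12.7, 15.9, 19.1 mm.
- Chance of a significant improvement when Acthar does nothing (200,000 simulated trials per case, normal changes, d = 20 mm):

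| k of 12 | Mean shift (mm) | SD 20 | SD 25 | SD 30 |
|---|---|---|---|---|
| 0 | 0 | 2.5% | 2.5% | 2.5% |
| 2 | 3.33 | 5.9% | 5.3% | 4.9% |
| 3 | 5.00 | 8.9% | 7.5% | 6.6% |
| 4 | 6.67 | 13.4% | 10.5% | 8.9% |
| 6 | 10.00 | 26.8% | 20.0% | 15.6% |

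With k = 3 and d from 15 to 30 mm, the chance is 7.2% to 12.4% at SD 20 and 5.4% to 9.0% at SD 30.

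**4. IOP.** If j participants receive a drug that lowers IOP by L mm Hg, the mean final change falls by j × L / 12. With j = 1 and L = 3 to 8 (assumed), that is 0.25 to 0.67 mm Hg.

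**The case against.** **Escalation rests on silence.** A reader might infer that the protocol permits background doses to be raised. It does not say so; it only fails to forbid it. Rescue, however, is expressly open, so the main point does not depend on this.

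**Withdrawal under section 7.2.** A participant whose dose changes arguably no longer satisfies criterion 4 and could be withdrawn. But that is at the investigator's discretion, treated participants who withdraw are replaced, and the SAP analyses completers. Using this route would add selection rather than handle the event.

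**Oral steroids and glaucoma drugs.** A reader might infer that stable users are admitted. Under a heading of exclusions, the unfinished sentence could equally list barred drugs. The text does not settle it, so the point rests on the three topical drugs and on rescue.

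**IOP.** A reader might infer that an added glaucoma drug hides a rise of 10 mm Hg. Section 9.4.3 has IOP measured at each visit and notes such rises, so one seen before the drug was added is still noted. Section 6.1.2 also allows Acthar to be stopped for glaucoma. Only the baseline-to-final comparison is exposed.

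**Direction.** Reducing background drops as symptoms improve would work against Acthar, and an added steroid could raise IOP. The bias favours Acthar for added or raised anti-inflammatories, not for every change.

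**Importance.** This is an unpowered pilot, and its limits are acknowledged in section 4.2. Large gains from drugs that these participants have already failed may be uncommon. Both points limit the weight of the table. They do not remove the bias, which affects a descriptive mean as much as a P-value.

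**Conclusion.** The point holds for the permitted topical drugs and for rescue: the stability condition ends at entry, rescue is unrestricted, and no rule covers later values. Improvement from an added or raised anti-inflammatory therefore counts as response to Acthar.

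Its size is unknown. The shifts and percentages above rest wholly on assumed numbers of participants, gains and SDs, and are not estimates for this trial.

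A reader might also infer that admitting loteprednol users is itself a flaw, because section 2.3.2 says "Acthar reduces inflammation in the body without synthetic steroids". That sentence describes mechanism. Adding Acthar to existing treatment in participants with persistent disease is compatible with the stated design; the weakness is the uncontrolled change during the study. Without a control, regression to the mean and natural variation would remain after any fix, but this source of bias can be reduced with data already being collected.

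**What to change.** 1. **Criterion 4 and section 6.5.** Require permitted background eye treatments to stay unchanged from Visit 1 through Visit 13. Complete the second sentence of criterion 4 so that oral corticosteroids and glaucoma drugs are clearly either excluded or allowed only if stable and unchanged.
2. **Section 6.5.1.** Name artificial tears as the permitted rescue. Allow any other drug when medically needed, and record it as a treatment change.
3. **Section 9.4.2 and SAP.** Do not credit improvement observed after an anti-inflammatory is started or raised. In the main analysis use the last value before the change, or else no improvement, with anyone who had worsened keeping the worse value. Choose one in advance. Show as-observed values as a sensitivity analysis, and report the number affected out of 12.
4. **Section 9.4.3.** Report added or increased IOP-lowering drugs beside the IOP results. Use the last IOP before the change for the baseline-to-final comparison, without counting each added drug as a 10 mm Hg event.

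The cost is a small protocol and SAP amendment and slightly tighter conduct. No new data items are needed, since concomitant and rescue drugs are already recorded. One practical limit: the schedule table shows staining at Visits 1, 3 (Day 14) and 13, so the last value before a later change may be an early one unless the participant is examined before the new drug starts.
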